To investigate in insufficient responders to the COBRA-Slim regimen if accelerated access to a six-month course of anti-TNF therapy (etanercept), is leading to improved remission rates when compared to conventional treatment adaptation according to the COBRA-Slim strategy, 28 weeks after randomization into one of two treatment arms.

Other secondary objectives:

1. To further determine the **clinical efficacy** of accelerated access to etanercept versus the standard COBRA-Slim strategy in terms of remission rates and functionality scales.
2. To compare **radiographic progression** between all treatment schemes.
3. To evaluate the side effects of the given treatments as evaluated according to the regulatory guidelines for marketed products.
4. To evaluate the primary outcome using the DAS28ESR instead of the DAS28CRP.

Other secondary exploratory objectives:

1. To further determine the **clinical effectiveness** of accelerated access to etanercept versus the standard COBRA-Slim strategy.
2. To evaluate treatment response based on a set of **PROs**.
3. Depending on the clinical results of the trial, a **health economic analysis** may be justified. This could be part of a health technology assessment project at KCE. Quality of life data as well as the national number of the participating patients are collected in this trial to facilitate a possible economic analysis.

All secondary and exploratory objectives will be assessed both for the insufficient responder population, as for the complete study population.

Outcome measures/endpoints

Primary outcome measure

Area under the curve of DAS28CRP over 104 weeks (long term effectiveness) in insufficient responders randomized to either COBRA-Slim Bio-Induction or Standard COBRA-Slim Induction.

Main secondary outcome measure

Proportion of insufficient responders achieving remission (DAS28CRP<2.6) 28 weeks after randomization (short term efficacy) to either COBRA-Slim Bio-Induction or Standard COBRA-Slim Induction.

Other secondary outcome measures

The following analyses will be performed in the randomized early insufficient responder population (w8-w32) with or without accelerated access to a six-month course of etanercept. The same analyses will also be performed including the randomized groups of insufficient responders, each completed with an early responder control population.

1. Clinical efficacy:
 - Remission (DAS28CRP<2.6) at w104.
 - EULAR response at 28 weeks after randomization and at w104

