 - HAQ response at 28 weeks after randomization and at w104
2. Radiographic progression: X-ray evolution at w52 and w104 compared to BL as reviewed and evaluated by the central team.
3. Side effects: (S)ARs from BL until w104
4. To evaluate the primary outcome using the DAS28ESR instead of the DAS28CRP.

Other secondary, exploratory outcome measures:

1. Clinical effectiveness:

A) In the randomized early insufficient responder population (w8-w32) with or without accelerated access to a six-month course of etanercept.

Effectiveness:

- AUC of DAS28CRP/DAS28ESR during 28 weeks after randomization
- Time to first remission during 28 weeks after randomization
- Sustained remission = remission for at least 24 weeks (BL-w104).
- Number of treatment changes, number of patients able to follow the protocol, number of patients using biologicals and/or GC at 28 weeks after randomization and at w104.
- Cumulative doses of GC and analgesic use at 28 weeks after randomization and at w104.

B) In the complete study population, including the randomized groups of insufficient responders, each completed with an early responder control population.

Effectiveness:

- Sustained remission = remission for at least 24 weeks (BL-w64, BL-w104, w64-w104).
- Number of treatment changes, number of patients able to follow the protocol, number of patients using biologicals and/or GC throughout the entire study

- Cumulative doses of GC and analgesic use throughout the entire study
- 2. Treatment response in terms of PROs:
 - Patient acceptable symptom state (PASS) and RA Impact of Disease (RAID) at 28 weeks after randomization and at w104
 - PASS at w64 and w104.
 - RAID at w 64, 104.
- 3. Cost-effectiveness:
 - WPAI / EQ5D questionnaire at 28 weeks after randomization and at w104
 - Per-protocol and out-of-protocol medication use as well as the number of outpatient visits and occasional hospitalization

[figure not shown]
Depending on the clinical results of the trial, a health economic analysis may be justified. This could be part of a health technology assessment project at KCE. Quality of life data as well as the national number of the participating patients are collected in this trial to facilitate a possible economic analysis.

3 Study design

Overall design

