In this pragmatic, prospective, multicenter, randomized, controlled trial of 2-year duration, 442 patients with early RA (≤ 1 year), previously untreated with DMARDs (disease modifying anti-rheumatic drugs), will be included. A subgroup of insufficient responders to the initial COBRA-Slim remission induction regimen will be randomly assigned, during a time window between w8 and w32, to 2 different treatment strategies.

Randomization will be balanced according to time-point of randomization, BL disease activity and RF/ACPA status using the minimization technique (see statistical plan). Patients who do not meet the criteria for randomization, during the so-called accelerated access period, will still follow the common adaptation strategy during the remaining part of the study.

Initial protocol-based treat to target period (BL until w32):

All participants will receive at BL a COBRA-Slim remission induction regimen, which includes:

- Methotrexate 15 mg PO weekly (starting from 10 mg weekly for 2 weeks)
- Step down scheme of GC: 30-20-12,5-10-7,5-5 mg prednisone PO daily, each for 7 days except for the lowest dose of 5 mg, this will be maintained until w28 and then tapered to 2.5 mg daily for two weeks before stopping completely.

In case at any evaluation moment from w4 until w32 (not included) patients do not reach low disease activity (LDA = DAS28CRP \leq 3.2), the MTX dose will be increased to 20 mg PO weekly.

If after this first adaptation patients still not achieve or maintain a sufficient response during the period from week 8 until 32 (the accelerated access period), they will be considered insufficient responders.

Insufficient responders are defined as:

Patients not reaching LDA (DAS28CRP \leq 3.2) at any evaluation moment from week 8 until 32 after the first adaptation (a previous MTX increase).

Patients not reaching remission (DAS28CRP $<$ 2.6) at the week 32 evaluation visit irrespective of a previous MTX increase.

These insufficient responders will be randomly assigned to one of two different treatment strategies:

Group 1: Standard COBRA-Slim Induction:

Addition of leflunomide 10mg PO daily as the next step in the protocol-based CareRA2020 treatment adaptation scheme.

If target of LDA is still not reached or maintained minimally 12 weeks after the initiation of Leflunomide, treatment has to be adapted according to the next step of the adaptation scheme.

Group 2: COBRA-Slim Bio-induction with accelerated access to anti TNF:

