The randomization scheme

Patients included in the trial and not achieving low disease activity (DAS28CRP \leq 3.2) between w8 and w32 or remission (DAS28CRP $<$ 2.6) at week 32, will be randomly assigned to one of two treatment groups (1:1 allocation):

- Group 1 stepping up to a combination of MTX with leflunomide as described in the standard COBRA-Slim strategy, or
- Group 2 receiving accelerated access to a 6 months course of etanercept (defined as etanercept or its biosimilars as marketed and reimbursed in Belgium) besides continued MTX therapy.

Randomization will be done electronically within the e-CRF whenever a patient is considered an insufficient responder within the time window from w8 until w32 included.

The randomization process will be balanced on the margins (minimization) according to time-point of randomization, BL disease activity and RF/ACPA status.

Patients who are not considered insufficient responders within the accelerated access period will be further followed in the protocol.

Method of implementing the allocation sequence

Each clinical site will be assigned a 3-digit site number, the patient numbers will start with this site number followed by a 3-digit patient number starting with 001.

At site, all study personnel (investigator and/or CTA) will be able to perform the randomization as long as this is clearly identified on the Delegation of Authority (DoA).

A patient identification and randomization list will be kept at site.

Blinding

No blinding is applicable in this trial, investigators and patients will know which medications and doses are taken.

Unblinding

Unblinding is not applicable.

Visits

In this trial two kinds of visits are defined: mandatory and optional.

Mandatory visits have to be performed for all included patients while optional visits are recommended but are not obligatory. These can be performed at the investigators discretion. The aim of these optional visits is to check if treatment adaptations have the required effect and for positive reinforcement in view of compliance.

In case patients are randomized, some optional visits are becoming mandatory (see table below) as will be shown in the patient schedule tab of the e-CRF. These visits are important for calculation of secondary outcomes.

Flowchart	Screen	BL	W4	W8	w12	W16	w20	w24	w28	w32	w36	W40	w44	w48	W52	w56	w60	w64
Randomized at W8	X	X	X	X		X		X		X	X	X			X			X
Randomized at W16	X	X	X	X		X	X			X	X	X	X		X			X

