In case NSAIDs or analgesics are used, these should be recorded for effectiveness evaluation, especially in relation to RA and RA related pain.

All study patients must receive oral folic acid supplements of minimally 1mg daily (except on day MTX is taken) as well as Calcium and vitamin D (minimal 1000 mg/800IU daily) as prophylactic treatment.

Trial restrictions

In- and exclusion criteria are clearly describing restrictions on inclusion of patients in the trial.

Assessment of compliance

Medications are prescribed according to the label and will be collected by the patients in their local pharmacy.

At each visit, patients will be questioned about medication intake. In this protocol, patients will be provided with a medication schedule/diary to follow.

In case of increased disease activity, patients will be inquired on their medication intake to pick up possible non-compliance.

9 Pharmacovigilance

Definition of an adverse event

An Adverse Event (AE) is defined as any untoward medical occurrence in a patient administered a pharmaceutical product. The occurrence does not necessarily have a causal relationship with this treatment. An AE can therefore be any unfavorable and unintended sign (including an abnormal laboratory finding), symptom, or disease temporally associated with the use of a medicinal product, whether or not related to the medicinal product.

The investigator and/or his study team will examine any patient experiencing an AE as soon as possible. The investigator will do whatever is medically necessary for the safety and well-being of the patient.

In this trial no adverse events have to be recorded in the e-CRF unless they are categorized as an adverse reaction, related to RA or RA treatment, or as an adverse event of interest as described further in the protocol.

Definition of an adverse reaction (AR)

All untoward and unintended responses to an investigational medicinal product or to an experiment and, when an investigational product is concerned, related to any dose administered.

The phrase "response to an investigational medicinal product" means that a causal relationship between a trial medication and an AE is at least a reasonable possibility, i.e. the relationship cannot be ruled out.

All cases judged by either the reporting medically qualified professional or the Sponsor as having a reasonable suspected causal relationship to the trial medication or to RA qualify as adverse reactions.

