In this trial only ARs and adverse events of interest, as defined above, will be captured in the e-CRF.

Following rules apply for reporting adverse events in the e-CRF:

- **After informed consent** has been obtained **but prior to initiation of study treatment**, only SAE of interest and ARs caused by a protocol-mandated intervention should be reported
- **After initiation of study treatment**, all ARs, serious adverse reaction (SARs), SUSARs and (serious) adverse events of interest will be recorded in the e-CRF up to the patient's final study visit.

In the e-CRF all above mentioned events will be detailed with the following information:

- Full details in medical terms and case description
- Duration of the event
- The action taken regarding the event
- The outcome of the event
- *Seriousness criteria (medical judgement of the treating investigator):*
 Seriousness will be evaluated for each adverse event based on the criteria described in the paragraph on definition of a serious adverse event. In case the seriousness is answered "yes" than the event should be reported within 24h.
- *Severity Grading for Adverse Events (medical judgement of the treating investigator):*
 Severity should be graded into one of the three classes that describe the clinical severity of the event as it occurred:
 - Mild (does not interfere with daily living)
 - Moderate (somewhat interferes with daily living or medications needed to relieve event)
 - Severe (incapacitating)
- *Causality grading (medical judgement of the treating investigator)*
 Causality should be graded, to determine to what extent the investigator thinks the adverse event is related to the proposed strategy, prescribed drugs or any other protocol-mandated intervention.
- For serious events: whether the event would be considered expected or unexpected according to the Reference Safety Information, which is the current version of the SmPc. *(medical judgement of the treating investigator)*.
- Outcome

Adverse events and reactions should be followed by the investigator until they have returned to normal or stabilized.

All events related to the normal disease course of RA, which are captured within the outcome parameters of the trial, are not considered as adverse events unless these events are considered by the investigator as adverse events of interest.

Reporting of adverse events that meet seriousness criteria:

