- A **Safety analysis** will include all treated patients, taking into account the treatment that they actually received. Any subject randomized into the study that received at least one dose of study drug will be included for safety analysis.

Statistical analysis plan

Summary of BL data and flow of patients

These BL variables, gathered at initiation of the COBRA-Slim remission induction regimen, will be used to assess comparability of the population eligible for randomization, and they will be reported as proportions or means with their standard deviations, when appropriate.

[figure not shown]

Overview of BL measurements.

Variable	Definition	Measurement level
Age		Continuous
BMI (kg/m ²) at BL	body mass index	Continuous
Gender		Dichotomous
Smoking status at BL	Status never-ever-current	Categorical
Alcohol intake at BL	consumption of any form of alcohol, units per week	Ordinal
Symptom duration at BL	time elapsed between onset of symptoms and BL	Continuous
Disease duration at BL	time elapsed between diagnosis of RA and BL	Continuous
Employed before symptom onset		Categorical
Employed at screening		Categorical
Comorbidities at screening		Categorical
RF positivity at BL	rheumatoid factor	Dichotomous
ACPA positivity at BL	Anti-citrullinated protein antibody	Dichotomous
Erosions present at BL		Dichotomous
Total TJC at BL	tender joint count	Continuous
Total SJC at BL	swollen joint count	Continuous
GA (0-100) at BL	Patient global assessment	Continuous
Pain (0-100) at BL	Visual analog scale of pain	Continuous
Fatigue (0-100) at BL	Visual analog scale of fatigue	Continuous
PhGA (0-100) at BL	physician global assessment	Continuous
ESR (mm/h) at BL	erythrocyte sedimentation rate	Continuous
CRP (mg/l) at BL	C-reactive protein	Continuous
DAS28ESR at BL	28 joint disease activity score (ESR)	Continuous
DAS28CRP at BL	28 joint disease activity score (CRP)	Continuous
HAQ score (0-3) at BL	Health Assessment Questionnaire	Continuous
EQ5D at BL	5 dimensions questionnaire for health-related quality of life	Continuous
RAID at BL	RA impact of disease score	Continuous
PASS at BL	Patient Acceptable Symptom State	Dichotomous

Flow Diagram

All values are an estimation taking into account the distribution present in CareRA. There were 21 failures at screening or randomization (6%) and we expect a drop-out rate of 21%.

Primary outcome analysis

Primary endpoint

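### The side-effect comparison of the randomised arms counts from baseline, 8 to 32 weeks before the arms exist, which dilutes relative measures of harm

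*Combined protocol and SAP*

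**What the plan says.** **Window and population.** Section 2, Other secondary outcome measures, gives the outcome as "Side effects: (S)ARs from BL until w104". The sentence that introduces the list reads "The following analyses will be performed in the randomized early insufficient responder population (w8-w32) with or without accelerated access", and the same analyses are then repeated with early responders added to each group.

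**When the arms begin.** Section 6, The randomization scheme, randomises "whenever a patient is considered an insufficient responder within the time window from w8 until w32 included". Before that, Section 3 states: "All participants will receive at BL a COBRA-Slim remission induction regimen". The first adaptation, a methotrexate increase, follows one rule for everyone.

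**Safety set.** Section 10, Subject populations, groups patients by the treatment they actually received and adds: "Any subject randomized into the study that received at least one dose of study drug will be included for safety analysis". This settles who is included. It does not say from what date events count.

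**RA-related events.** Section 9, Definition of an adverse reaction, says that cases judged as "having a reasonable suspected causal relationship to the trial medication or to RA qualify as adverse reactions". Later in Section 9, Collecting and Reporting of adverse events, a rule opens with "All events related to the normal disease course of RA, which are captured within the outcome parameters of the trial, are not considered". Under that rule such events fall outside the adverse event count, with an exception for events of interest.

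**Status.** Section 10, Secondary outcome analysis, makes every secondary outcome other than the main one exploratory, to be reported as estimates with 95% intervals and without significance claims.

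**The concern.** A comparison of harm between two arms should count events that the assignment could have influenced. Here the count opens at the start of induction, when no patient has an arm. The five prednisone steps above 5 mg last 7 days each, 35 days in all, so they are finished before the earliest randomisation at week 8. Any reactions they cause enter both arms alike. Events common to both arms shrink any relative measure, and for harm an error toward no difference is false reassurance. Because these outcomes are reported only as estimates with intervals, the diluted estimate is what the reader receives.

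Other outcomes in the same section, such as EULAR and HAQ response, are already timed from randomisation, so the plan has the convention it needs.

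A second, smaller matter is that the two Section 9 rules give different answers on whether an RA-related event is an adverse reaction. The content of the outcome therefore depends on which rule is applied.

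**Working it through.** **Plan's own figure.** The plan states no reaction rate, sample size or power for side effects, so there is nothing to reproduce on this point. Its primary-endpoint size does reproduce (difference 70, SD 103: a t-test needs 34.97 per arm, 70 in total; 82 completers give 86.0% power), but it does not bear on this question.

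**Inputs from the protocol.** Window 104 weeks (Section 2); randomisation week R from 8 to 32 (Section 6); 104 patients randomised, so 52 per arm (Section 10, Sample size calculation).

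**Assumptions.** RR is the true post-randomisation rate ratio. k is the pre-randomisation rate divided by the later control rate. The documents give neither, so ranges are shown.

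**1. Shared time.** f = R/104: 8/104 = 7.7%, 16/104 = 15.4%, 24/104 = 23.1%, 32/104 = 30.8%.

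**2. Ratio seen when counting from baseline.** [k·f + (1−f)·RR] / [k·f + (1−f)].

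- Example, R = 32, k = 1, RR = 2: (0.308 + 0.692 × 2)/1 = 1.69.
- Example, R = 32, k = 2, RR = 1.5: (0.6154 + 1.0385)/(0.6154 + 0.6923) = 1.26.

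| True RR | k | All randomised at w8 | All randomised at w32 |
|---|---|---|---|
| 1.5 | 1 | 1.46 | 1.35 |
| 1.5 | 2 | 1.43 | 1.26 |
| 1.5 | 3 | 1.40 | 1.21 |
| 2.0 | 1 | 1.92 | 1.69 |
| 2.0 | 2 | 1.86 | 1.53 |
| 2.0 | 3 | 1.80 | 1.43 |

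**3. Differences.** With λ the control rate per 104 weeks, the expected count difference per patient is [k·f·λ + (1−f)·RR·λ] − [k·f·λ + (1−f)·λ] = (1−f)(RR−1)λ. The early term cancels, so the difference in total counts is unchanged. Two things do change:

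- Expressed as a rate over the full 104 weeks, the difference is the true rate difference times (1−f), that is 0.923 (w8) to 0.692 (w32) of it.
- With Poisson counts, the standard error of the count difference grows by √[1 + 2kf/((1−f)(1+RR))]. For k = 1 and RR = 2 this is √(1 + 0.1538/2.7692) = 1.03 at w8 and √(1 + 0.6154/2.0769) = 1.14 at w32.

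**4. Any-event proportions.** p = 1 − exp(−expected count), with λ = 0.5 and RR = 2 assumed, 52 per arm and no dropout. Differences are taken before rounding.

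| Randomised at | Count from | Control | Etanercept | Difference (points) | Power, two-sided 5% |
|---|---|---|---|---|---|
| w32 | randomisation | 29.3% | 50.0% | 20.7 | 58% |
| w32 | baseline, k = 1 | 39.3% | 57.1% | 17.7 | 44% |
| w32 | baseline, k = 3 | 55.4% | 68.5% | 13.0 | 28% |
| w8 | randomisation | 37.0% | 60.3% | 23.3 | 67% |
| w8 | baseline, k = 1 | 39.3% | 61.8% | 22.4 | 63% |
| w8 | baseline, k = 3 | 43.8% | 64.6% | 20.8 | 57% |

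No test is planned on this outcome; power is used here only to gauge lost information.

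**5. The two RA rules side by side.** Under the definition, a causal link to RA alone is enough to make an event an adverse reaction. Under the collection rule, an RA-course event already captured by an outcome parameter is not an adverse event at all, unless it is an event of interest. The rules disagree on captured RA events. RA-related events that no outcome parameter captures still count under the definition. The same collection section has the investigator grade relation to the strategy, the prescribed drugs or another protocol intervention, so treatment-related events can be picked out at analysis. It lists no separate grading of relation to RA.

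**The case against.** The strongest reply has five parts.

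- **The dilution depends on the measure.** The plan names no ratio. This stands in part: the expected difference in total counts is not diluted, and at week 8 with equal rates the loss is small (1.5 to 1.46). The larger figures need late randomisation or a higher early rate, and the documents give no distribution of randomisation times.
- **Baseline is the natural origin for the complete population.** Early responders are split into complementary subgroups only at week 32, and the primary AUC also runs from baseline. This stands for the whole-cohort description. It does not justify using the same window to contrast the randomised arms.
- **The safety analysis goes by treatment received.** That does not repair the window: no rule assigns events to treatment periods. Nor would counting by arm isolate the drugs, because Table 1 lets the standard arm move to etanercept and the other arm to leflunomide. Both summaries are needed, and the by-arm one compares strategies.
- **The outcome is exploratory, and the matching objective speaks of evaluating side effects.** The status is right and limits the weight of the point. The outcome is nevertheless listed for the groups with and without accelerated etanercept and reported as an effect estimate.
- **The RA-event rules are mostly harmless.** A reader might infer that the better-controlled arm will look safer because RA events count as reactions. The documents do not show this. Captured RA-course events are excluded by the collection rule, the outcome parameters are broad (DAS28, HAQ, X-ray, RAID, PASS), and causality to treatment is already graded. What remains is a conflict of wording with no demonstrable size.

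**Conclusion.** The point holds for the comparison of the randomised insufficient-responder arms. As written, 7.7% to 30.8% of the counted window precedes assignment, and this share comes straight from the protocol. Its effect on estimates rests on assumed rates: with equal early and later rates, a true ratio of 2.0 appears as 1.92 to 1.69 and 1.5 as 1.46 to 1.35; with an early rate twice the later control rate, 1.5 appears as 1.43 to 1.26.

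A reader might go further and infer a bias favouring one arm, a threat to the primary result, or a fault in collecting reactions from baseline. None follows. Pre-randomisation events are balanced in expectation, the primary endpoint does not use them, and collection from the start of treatment is right for the cohort. Nor is this the trial's only safety information, since safety analyses are planned for both populations and events of interest are collected as well. The RA-event rules are a separate matter of consistency.

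**What to change.** 1. For the comparison of the randomised insufficient-responder arms, count (S)ARs and events of interest from randomisation to week 104, as rates per patient-year by randomised arm. Present this alongside the treatment-received safety analysis of Section 10.
2. Report events from baseline to randomisation once, pooled over arms.
3. Keep the baseline-to-week-104 window for describing the complete study population.
4. Confirm that the e-CRF captures the onset date of each event; Section 9 lists duration only.
5. Reconcile the two Section 9 rules on RA-related events. For the arm comparison, use the existing causality grading to select treatment-related events, and report RA-related events apart.

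**Cost.** Changed wording in Sections 2, 9 and 10 (by protocol amendment, as Section 10 requires for changes to the statistical plan), one extra table, and an onset-date field if none exists. The arm comparison will contain somewhat fewer events, but those dropped occurred before assignment and say nothing about the arms.

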	
Initial protocol-based treat to target period (BL until w32)
 
In this pragmatic, prospective, multicenter, randomized, controlled trial of 2-year duration, 442 patients with early RA (≤ 1 year), previously untreated with DMARDs will be included. All participants will receive at baseline (BL) a COBRA-Slim remission induction regimen, consisting of MTX 15 mg Per Os (PO) weekly, with a step-down scheme of GC (30-20-12,5-10-7,5-5 mg prednisone PO daily, each for 7 days except for the lowest dose of 5 mg, which will be maintained until w28 and then tapered to 2.5 mg daily for 2 weeks before stopping completely).
 
In case at any evaluation moment from w4 until w32 (not included) patients do not reach low disease activity (LDA = DAS28CRP≤ 3.2), the MTX dose will be increased to 20 mg PO weekly.
 
If after this first adaptation patients still not achieve or maintain a sufficient response during the period from week 8 until 32 (the accelerated access period), they will be considered insufficient responders.
 
Insufficient responders are defined as:
 
 - Patients not reaching LDA (DAS28CRP≤ 3.2) after the first adaptation (MTX increase) at any evaluation moment from week 8 until 32 - Patients not reaching remission (DAS28CRP< 2.6) at the week 32 evaluation visit irrespective of a previous MTX increase 
These insufficient responders will be randomly assigned to one of two different treatment strategies:
 
Group 1: Standard COBRA-Slim Induction: Addition of leflunomide 10mg PO daily as the next step in the protocol-based CareRA2020 treatment adaptation scheme.
 
Group 2: COBRA-Slim Bio-induction with accelerated access to anti-TNF (etanercept): Etanercept is defined as etanercept or its biosimilars marketed and reimbursed in Belgium. Addition of etanercept 50mg Subcutaneous (SC) weekly for a period of 24 weeks in this accelerated access arm as the next treatment adaptation.

--	---

Randomization will be balanced according to time-point of randomization, baseline (BL) disease activity and Anti-Citrullinated Protein Antibody (ACPA) and Rheumatoid Factor (RF) status to ensure comparability of the treatment groups with respect to these prognostic variables.

Patients who do not meet the criteria for randomization, during the so-called accelerated access period, will all follow the same Standard COBRA-Slim treatment adaptation scheme, further detailed in the protocol.

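### Exploratory sustained remission in the randomised arms is counted from baseline, so some week-32 entrants can already be successes before allocation, which slightly dilutes the contrast

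*Combined protocol and SAP*

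**What the plan says.** **Outcome.** Section 2, item 1A covers the population described as "In the randomized early insufficient responder population (w8-w32) with or without accelerated access to a six-month course of etanercept". One of its outcomes is "Sustained remission = remission for at least 24 weeks (BL-w104"). The parallel line in item 1B, for the complete population, reads "Sustained remission = remission for at least 24 weeks (BL-w64, BL-w104, w64-w104"). This shows that the bracket is an observation window. Other 1A outcomes are tied to allocation, for example "Time to first remission during 28 weeks after randomization". No section excludes remission before randomisation from the sustained-remission outcome.

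**Entry at week 32.** The Trial Summary counts as insufficient responders "Patients not reaching remission (DAS28CRP< 2.6) at the week 32 evaluation visit". Section 3 says the rule applies "at the week 32 evaluation visit irrespective of a previous MTX increase". Section 6 (The randomization scheme) has patients randomised "whenever a patient is considered an insufficient responder within the time window from w8 until w32 included".

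**Treatment before week 32.** All patients share the COBRA-Slim induction. Its lowest prednisone dose follows the scheme "this will be maintained until w28 and then tapered to 2.5 mg daily for two weeks before stopping completely" (section 3).

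**Visits.** The visits listed for the primary model in section 10 are weeks 4, 8, 16, 24, 32 and later. Weeks 12, 20 and 28 are optional (section 6, Visits).

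**The concern.** A between-arm comparison should count only what can follow from allocation. Here a patient can be in remission for most of the induction phase, lose it at week 32, be randomised as an insufficient responder, and already hold a completed 24-week remission. No later relapse removes that success, and neither strategy contributed to it.

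The primary AUC also starts at baseline but behaves differently. AUC is additive, so shared time before randomisation adds the same expected amount to both arms and leaves the absolute difference intact. An ever-achieved binary outcome does not have this property: a patient already counted as a success cannot show a treatment difference.

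What is at stake is the size of one reported effect estimate. The plan relies on effect sizes with 95% confidence intervals for its exploratory outcomes, so any dilution goes straight into the published figure.

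**Working it through.** The plan gives no rate, sample size or power for sustained remission, so there is no figure to reproduce. The check is whether 24 weeks fit before randomisation, and what follows if they do.

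**1. Which entrants.** Before week 32, section 3 requires a missed low-disease-activity target, then an MTX increase, then a second miss. On DAS28CRP, a patient continuously in remission from baseline or week 4 has not triggered the increase, so a first miss at week 28 leads to the increase and not to randomisation. Entry at week 24 or earlier leaves at most 20 weeks between baseline and the last visit before randomisation. The route is therefore confined to week-32 entrants.

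**2. Spans available to a week-32 entrant (nominal weeks).**

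| Remission observed at | Span | Condition |
|---|---|---|
| w4 to w24, mandatory visits only | 24 − 4 = 20 | falls short |
| w4 to w28 | 28 − 4 = 24 | optional w28 visit held |
| baseline to w24 | 24 − 0 = 24 | already in remission at baseline |
| w8 to w24, credited to w32 | 32 − 8 = 24 | spell counted to the first failing visit, a rule the protocol does not state |

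Remission at baseline is possible on paper: the inclusion criteria set no minimum disease activity, and the minimisation table has a category for DAS28CRP of 3.2 or below.

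**3. Effect on the contrast.** Let f be the share already successful in each arm, and q1 and q2 the later success probabilities. The observed rate in each arm is f + (1 − f)q, so the observed difference is (1 − f)(q2 − q1). This assumes that the early successes would otherwise have shown the same between-arm difference as the other patients.

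**4. Size of f (assumed, not in the documents).** A simulation used assumed DAS28CRP courses (between-patient SD 0.9, within-patient SD 0.5–0.7, six scenarios, 400,000 patients each) with the protocol's entry rules. Strict counting from w4 to w28, with w28 attended, gave 5–11% of week-32 entrants, or 1–4% of all randomised patients. The second share depends on how many patients enter at week 32, which the documents also do not give.

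**5. Result, with assumed rates of 40% v 60%.**
- f = 1%: 0.01 + 0.99 × 0.40 = 40.6%, and 0.01 + 0.99 × 0.60 = 60.4%. The difference is 19.8 points.
- f = 4%: 0.04 + 0.96 × 0.40 = 42.4%, and 0.04 + 0.96 × 0.60 = 61.6%. The difference is 19.2 points.

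With the 104 randomised patients in the sample size table, 1–4% is about 1 to 4 patients.

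**6. Against sampling error.** With 52 per arm and the same rates, the 95% half-width is 1.96 × √(2 × 0.24 / 52) = 0.188, or about 19 points. The shift of 0.2–0.8 points is far smaller.

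**The case against.** The strongest reply is that the effect is too small to matter. Section 10 treats the outcome as exploratory and reserves significance testing for the primary and main secondary endpoints. The interval is far wider than the shift, and the early successes are expected equally in both arms. If these patients would regain remission easily under either strategy, the loss is smaller still. All of this stands.

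A second reply is that a baseline window is deliberate, because the primary outcome measures disease burden over the first two years and other outcomes are already anchored at randomisation. This stands in part. It explains a baseline window for describing the cohort, but not for comparing an ever-achieved binary outcome between arms.

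Some stronger readings are tempting, and the documents do not support them:

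- **A reader might infer that a large share of patients is affected.** Counting a spell to the first failing visit gives 20–30% of week-32 entrants, or 5–11% of all randomised patients, in the same simulation. A 20-point difference would then fall to 19.0–17.8. That rule appears nowhere in the protocol, and it credits weeks 24 to 32 as remission although week 32 is the failing visit. Even the strict figure needs the optional week-28 visit.
- **A reader might infer that every non-remitter at week 32 is randomised.** Section 3 (General rules for treatment adaptations) exempts patients whose last adaptation has not reached full strength. The Trial Summary's population and objective entries also describe insufficient response only as DAS28CRP above 3.2, which would narrow the route. These entries and the week-32 remission rule should be reconciled.
- **A reader might infer that no remission spell can straddle randomisation.** Section 3 lets DAS44 replace DAS28CRP when isolated foot involvement makes DAS28CRP too low. A patient could therefore be randomised with DAS28CRP below 2.6.

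**Conclusion.** The point holds as a minor flaw in one exploratory outcome definition. Item 1A lets some week-32 entrants count as sustained-remission successes before they receive any allocated treatment.

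The expected effect is dilution by about (1 − f). With f of about 1–4%, a 20-point difference becomes 19.2–19.8 points. This rests on assumed disease courses, attendance at the optional week-28 visit, strict visit-to-visit counting, and an otherwise equal between-arm difference in the affected patients. Larger values depend on a counting rule that the plan does not state.

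A reader might infer bias in favour of one strategy. The documents do not support this: allocation is random and minimised on time-point of randomisation, so early successes are expected equally in both arms. The primary and main secondary conclusions are unaffected.

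**What to change.** In section 2, item 1A, change the window to run from the randomisation visit to week 104, and count only remission time from that visit onward. The second clause also settles the rare patient randomised on DAS44 with DAS28CRP below 2.6: remission before the visit is not credited. Keep the baseline windows in item 1B for the complete population. It would also help to state how a spell is counted between visits and when an optional visit is missing.

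The change needs no new data or visits. A 24-week remission stays attainable for everyone: 104 − 32 = 72 weeks remain for week-32 entrants and 104 − 8 = 96 for week-8 entrants. This unequal follow-up by entry time is a drawback, but minimisation on time-point balances it between arms. The other cost is a protocol amendment, which section 10 (Other statistical considerations) requires for any departure from the statistical plan.
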